10.3.1 Recording of response in the eCRF

The applicable overall response category for each visit that includes disease assessment must be recorded in the eCRF.

10.3.2 Other definitions of outcome

- **Toxic death:** Any death to which drug toxicity is thought to have a major contribution.
- **Early death:** Death during the first 28 days of treatment.

11 PATIENT WITHDRAWAL BEFORE COMPLETION OF TREATMENT SCHEDULE

The Investigator must make every reasonable effort to keep each patient on trial for the whole duration of the trial (i.e. until 28 ± 7 days after last BT1718 administration). However, if the Investigator removes a patient from the trial or if the patient declines further participation, final 'off-study' assessments should be performed ideally before any subsequent therapeutic intervention. All the results of the evaluations and observations, together with a description of the reasons for withdrawal from the trial, must be recorded in the medical records and in the eCRF.

Patients who are removed from the trial due to adverse events (clinical or laboratory) will be treated and followed according to accepted medical practice. All pertinent information concerning the outcome of such treatment must be recorded in the eCRF and on the serious adverse event (SAE) report form where necessary.

The following are justifiable reasons for the Investigator to withdraw a patient from the trial.

- Adverse Event (AE)/SAE;
- Withdrawal of consent;
- Serious deviation from the trial protocol (including persistent patient attendance failure and persistent non-compliance);
- Sponsor's decision to terminate the trial;
- Withdrawal by the Investigator for clinical reasons not related to BT1718;
- Evidence of disease progression;
- Pregnancy (for female patients during the study)

12 DEFINING THE END OF TRIAL

The 'end of trial' is defined as the date when the last patient has completed the 'off-study' visit or the final follow-up (whichever is the latter). The 'off-study' visit is scheduled to take place 28 +/-7 days after the last dose of BT1718 administration. End of trial may only be declared when all patients have either withdrawn from the trial, died, or completed a minimum of 12 months survival follow-up since their first administration of BT1718.

IMP will be available for two years from the latest date that any remaining patients started treatment. After this, any remaining patients will come off-study and the trial will end as above.

The end of trial cannot be declared while any patient is still having study visits or while study data are still being collected, e.g. progression-free or OS data.

If an arrangement becomes possible where patients can continue on prolonged or extended use of IMP, beyond the end of trial, that arrangement will be distinct from the trial and will not prevent the end of trial being declared.

It is the responsibility of the CDD to inform the MHRA and the REC within 90 days of the 'end of the trial' that the trial has closed.

In cases of early termination of the trial (for example, due to toxicity) or a temporary halt by the CDD, the CDD will notify the MHRA and the REC within 15 days of the decision and a detailed, written explanation for the termination/halt will be given.

Recruitment will cease when:

- The drug is considered too toxic to continue treatment before the required number of patients have been recruited.
- The stated number of patients to be recruited has been reached.
- The stated objectives of the trial are achieved.
- The stated objectives of the trial are likely to be met but the trial is stopped due to lack of efficacy (the trial will be closed to recruitment on the date of this decision).

Regardless of the reason for termination, all data available for patients at the time of discontinuation of follow-up must be recorded in the eCRF. All reasons for discontinuation of treatment must be documented.

In terminating the trial, the Sponsor and the Investigators must ensure that adequate consideration is given to the protection of the patient's interest.

13 DATA ANALYSIS AND STATISTICAL CONSIDERATIONS

The final analysis will be conducted after one of the following conditions is met:

- The trial is terminated early
- The end of trial as defined in Section 12 has been reached.

13.1 Sample size

Phase I, dose escalation phase

The number of patients required for the phase I will depend on the number of dose levels required to be explored to determine the MTD. It is anticipated that approximately 50 to 60 patients will be entered between Stages 1 and 2, the final number will depend on the number of dose escalations required and the number of evaluable patients.

Phase I of the trial has completed.

Phase IIa, expansion phase

Squamous NSCLC cohort – approximately 16 evaluable patients with squamous NSCLC will be recruited in this cohort to further characterise the tolerability of the RP2D in this population and an early exploration of clinical and biological activity.

Basket cohort – approximately 16 evaluable patients with advanced solid tumours will be recruited in this cohort to further characterise the tolerability of the RP2D in this population and an early exploration of clinical and biological activity.

Squamous oesophageal cancer cohort – following review of data obtained from the squamous NSCLC and basket expansion cohorts by the Joint Development Committee a as described in Section 3.2, approximately 16 evaluable patients with squamous oesophageal cancer may be recruited in this cohort to further characterise the tolerability of the RP2D in this population and an early exploration of clinical and biological activity. Other tumour types with a high incidence of MT1-MMP expression may be considered in future expansion cohort(s) and would be specified in a future amendment.

To assess clinical activity, objective response rate will be considered in terms of the confidence in excluding activity at a desired response rate (e.g. >30-40%) and for exceeding an undesirable response rate (e.g. <10-20%), reflecting an A'Hern single-stage clinical trial model for binomial distributions, with the Sargent three-outcome approach describing intermediate results. In a 16 patient cohort, less than 3 responses would exclude a response rate of 30% with 80% power, while 3 or more responses would indicate a response rate of 10% or greater with a significance level of 0.2. Similarly, less than 5 responses would exclude a response rate of 40% with 80% power, while 5 or more responses would indicate a response rate of 20% or greater with a significance level of 0.2. Hence 16 patients is a reasonable cohort size to permit some comparison of observed response rates against such benchmarks.

Activity within the squamous NSCLC and/or basket cohorts will be considered in the decision to begin enrolment in the squamous oesophageal cancer cohort

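### Section 13.1 gives both 16-patient response rules 80% power and a 0.2 significance level, but the exact values are 0.90 and 0.21 for the first rule and 0.83 and 0.20 for the second

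*Protocol*

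**What the plan says.** Protocol section 13.1 plans about 16 evaluable patients in each Phase IIa cohort. It judges the objective response rate against a desired and an undesirable rate, "reflecting an A'Hern single-stage clinical trial model for binomial distributions", and uses a three-outcome approach to describe intermediate results.

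It states two rules for a cohort of 16:

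- **10% against 30%.** "less than 3 responses would exclude a response rate of 30% with 80% power", and "3 or more responses would indicate a response rate of 10% or greater with a significance level of 0.2".
- **20% against 40%.** "less than 5 responses would exclude a response rate of 40% with 80% power", and "5 or more responses would indicate a response rate of 20% or greater with a significance level of 0.2".

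It then concludes: "Hence 16 patients is a reasonable cohort size to permit some comparison of observed response rates against such benchmarks". It does not say that the power and significance figures are approximate, rounded or minimum values.

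**The concern.** The two rules differ in cut-off and in benchmark rates, yet they carry identical operating characteristics. With 16 patients the response count takes few values, so a cut-off rarely lands exactly on round error rates, and two different rules would hardly both do so. The figures look like design targets reported as if they were what the rules achieve.

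These are the only numerical operating characteristics in the protocol, and the cohort-size conclusion is drawn directly from them. The 10% and 30% pair matters most: sections 2.1.1 and 2.1.2 use about 10% as the chemotherapy comparator and 30% as the aim, for squamous NSCLC and squamous oesophageal cancer respectively. Anyone weighing a cohort with two or fewer responses would take from section 13.1 that a drug with a true 30% rate had a one-in-five chance of such a result. The exact chance is about half that.

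**Working it through.** **Inputs, all from section 13.1.** n = 16. Rule A: positive if X ≥ 3, undesirable rate 0.10, desired rate 0.30. Rule B: positive if X ≥ 5, undesirable rate 0.20, desired rate 0.40. Stated for both: power 80%, significance level 0.2. The model is single-stage exact binomial, one-sided.

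**Formulas.** With X ~ Binomial(16, p) and cut-off r:

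- type I error = P(X ≥ r | undesirable rate) = 1 − P(X ≤ r − 1 | undesirable rate)
- power = P(X ≥ r | desired rate) = 1 − P(X ≤ r − 1 | desired rate)

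**Rule A (r = 3).**

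- At 10%: P(0) + P(1) + P(2) = 0.1853 + 0.3294 + 0.2745 = 0.7892. Type I error = 0.2108.
- At 30%: 0.0033 + 0.0228 + 0.0733 = 0.0994. Power = 0.9006.

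**Rule B (r = 5).**

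- At 20%: P(0) to P(4) = 0.0281 + 0.1126 + 0.2111 + 0.2463 + 0.2001 = 0.7982. Type I error = 0.2018.
- At 40%: 0.0003 + 0.0030 + 0.0150 + 0.0468 + 0.1014 = 0.1666 (summed before rounding). Power = 0.8334.

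| Rule | Type I error, stated | Type I error, exact | Power, stated | Power, exact |
|---|---|---|---|---|
| ≥3/16, 10% against 30% | 0.2 | 0.211 | 0.80 | 0.901 |
| ≥5/16, 20% against 40% | 0.2 | 0.202 | 0.80 | 0.833 |

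**Can the stated pair of figures be reproduced another way?** None of the variants tried gives 0.2 with 80% for either rule:

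| Variant | Rule A: type I error / power | Rule B: type I error / power |
|---|---|---|
| Normal approximation, no continuity correction | 0.122 / 0.837 | 0.130 / 0.763 |
| Normal approximation, with correction | 0.227 / 0.895 | 0.208 / 0.834 |
| Strictly more than 3 or 5 responses | 0.068 / 0.754 | 0.082 / 0.671 |

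Mid-p type I errors are 0.140 and 0.142.

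**Size of the discrepancy.** Rule A's power is 10.1 percentage points above the stated value, so its false-negative risk is 0.099 against an implied 0.20. Rule B's power is 3.3 points above. The type I errors exceed 0.2 by 0.011 and 0.002.

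**The case against.** The case for leaving the text alone has real force:

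- **Rounding.** The significance level is given to one decimal, and both 0.211 and 0.202 round to 0.2. This stands. For the second rule there is nothing to correct in the type I error beyond showing another digit.
- **Direction.** Read as a minimum, 80% power is met by both rules. The exclusion statements also hold: the one-sided 80% upper limit is 24.9% for 2/16, below 30%, and 38.5% for 4/16, below 40%. This stands as a limit on the weight, but the text does not call 80% a minimum, and rounding cannot turn 90% into 80%.
- **Role of the figures.** Response is a secondary objective (section 3.1.2), data are presented descriptively (section 13.2), and 95% confidence intervals will be reported (section 13.6). This also stands; no primary conclusion depends on the figures.

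Three stronger readings are tempting, and the protocol does not support them.

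- A reader might infer that 16 is the wrong size, because no cut-off at 16 keeps type I error at or below 0.2 with power of at least 80%. Taken strictly that is true (≥4/16 gives 0.068 and 0.754; ≥6/16 gives 0.082 and 0.671). For the second pair, however, it rests on an excess of 0.0018, and section 13.1 claims only that 16 permits some comparison.
- A reader might infer an inflated false-positive risk across cohorts, since "Activity within the squamous NSCLC and/or basket cohorts will be considered in the decision to begin enrolment in the squamous oesophageal cancer cohort". But activity is only considered there, and section 3.2 leaves the opening of the oesophageal cohort to a committee review of the data. No response count is a binding trigger, and the protocol gives no 10% comparator for the mixed-tumour basket. A cross-cohort error rate would therefore describe a rule that the protocol does not contain.
- A reader might infer that 15 patients would be better, since ≥3/15 gives 0.184 and 0.873. That would lower the ≥5 rule's power at 40% to 0.783.

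**Conclusion.** The figures are wrong as written, and the point is minor. Under the model that section 13.1 names, the rules deliver 0.21 and 0.90 (three or more of 16) and 0.20 and 0.83 (five or more of 16), where the text gives 0.2 and 80% for each. The one material error is the first rule's power, which is understated by about 10 points. The second rule's power is understated by about 3 points, and the first rule's type I error is slightly understated.

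This rests on exactly 16 evaluable patients, independent binomial responses and one-sided exact tails. The conclusion that 16 is a reasonable cohort size survives; on power, the exact figures support it better than the printed ones.

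**What to change.** In section 13.1, replace the shared 80% and 0.2 with the values for each rule: three or more of 16 has type I error 0.21 at 10% and power 0.90 at 30%; five or more of 16 has type I error 0.20 at 20% and power 0.83 at 40%.

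Optionally, because cohorts are only approximately 16, add the values for nearby evaluable numbers with the cut-offs held fixed (same formulas, n changed):

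| Evaluable n | ≥3: type I error at 10% | ≥3: power at 30% | ≥5: type I error at 20% | ≥5: power at 40% |
|---|---|---|---|---|
| 14 | 0.158 | 0.839 | 0.130 | 0.721 |
| 15 | 0.184 | 0.873 | 0.164 | 0.783 |
| 16 | 0.211 | 0.901 | 0.202 | 0.833 |
| 17 | 0.238 | 0.923 | 0.242 | 0.874 |
| 18 | 0.266 | 0.940 | 0.284 | 0.906 |

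The table could equally sit in the SAP. The cost is two reworded sentences and, if wanted, five table rows. No patients are added, and the cohort size and cut-offs stay as they are.

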13.2 Presentation of data

Data will be presented in a descriptive fashion. Variables will be analysed to determine whether the criteria for the trial conduct are met. This will include a description of patients who did not meet all the eligibility criteria, an assessment of protocol deviations, IMP accountability and other data that impact on the general conduct of the trial.

Baseline characteristics will be summarised for all enrolled patients. Patients who died or withdrew before treatment started or did not complete the required safety observations will be described and evaluated separately.

Treatment administration will be described for all cycles. Dose administration, dose modifications or delays and the duration of therapy will be described.

13.3 Safety

Safety data will be collected from the date of written consent. Safety variables will be summarised by descriptive statistics. Laboratory variables will be described using NCI CTCAE Version 4.02.

Adverse events will be reported for each dose level and presented as tables of frequency of AEs by body system and by worse severity grade observed. Tables should indicate related and unrelated events.

13.4 Pharmacokinetics

The plasma concentration/time data will be analysed using non-compartmental methods. The PK parameters to be determined for intact BT1718 include C_{max}, AUC, t_{1/2}, AUC, t_{1/2},

13.5 Pharmacodynamics

13.6 Anti-tumour activity

Documenting anti-tumour activity is a secondary objective of this trial. Patients must receive \geq 66% of the planned dose exposure of BT1718 within Cycle 1 and 2, or at least one full cycle and have a baseline assessment of disease and at least one repeat assessment to be evaluable for response. Patients in the expansion phase must meet the MT1-MMP positivity rate to be evaluable for this objective. Objective responses, the best tumour response achieved by each patient while on trial and the time to progression will be presented in the data listings by cohort.

The response rate (proportion of evaluable patients with objective response) will be reported by cohort. Progression free survival will be calculated from trial entry until the time of documented disease progression or death (whichever occurs first). Patients who are alive and progression free or lost to follow up at the time of analysis will be censored at the time the patient was last known to be alive and progression free. Overall survival will be calculated from trial entry until the time of death from any cause. Patients who are alive or lost to follow up at the time of analysis will be calculated from trial entry until the time of death from any cause. Patients who are alive or lost to follow up at the time of analysis will be censored at the time the patient was last known to be alive. Duration of response will be measured from the date of the first scan where response was seen until date of first RECIST V1.1 progression or death. Median PFS, OS and duration of response will be presented. The PFS and OS rate at 6 months will also be presented. 95% confidence intervals will be reported.

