3.5 Patient evaluability

3.5.1 Response

All patients who meet the eligibility criteria and receive at least one full cycle of IMP or ≥66% of the planned dose exposure of BT1718 within Cycle 1 and 2, and have a baseline assessment of disease and at least one repeat disease assessment will be evaluable for response.

In the expansion cohorts, baseline MT1-MMP H-score must also meet the positivity criteria for the patient to be evaluable.

Repeat assessments after at least four weeks are required in order for a patient to be confirmed as having a complete or partial response (CR or PR). To be assigned a status of stable disease (SD), follow-up measurements must have met the SD criteria at least once and at least six weeks after the initial dose of BT1718 is given.

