5.6.1.2 Phase II, expansion phase

Patients will be replaced in the expansion cohorts if they receive less than one full cycle and less than 66% of the planned dose exposure of BT1718 within Cycle 1 and 2 for reasons other than drug-related (probably or highly probably) toxicity. Patients will also be replaced if retrospective MT1-MMP testing identifies that their baseline tumour sample had a low MTI-MMP H-score.

Replacement of patients will be confirmed by the Sponsor. There may be circumstances based on the emerging data from the trial or BT1718 availability that result in a patient not being replaced. This will be documented by the Sponsor.

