10.3 Tumour response

All patients who meet the eligibility criteria and receive \geq 66% of the planned dose exposure of BT1718 within Cycle 1 and 2, or at least one full cycle and have a baseline assessment of disease and at least one repeat disease assessment will be evaluable for response. Patients who develop clear evidence of PD without a formal disease assessment will be considered non-responders. Confirmatory repeat assessments are required at least four weeks after an initial indication of CR or PR, in order for the

patient to be assigned a status of confirmed CR or PR. To be assigned a status of SD, follow-up measurements must have met the SD criteria at least once and at least six weeks after the initial dose of BT1718 is given.

Should rapid tumour progression occur before the completion of four weeks the patient will be classified as having early progression.

Tumour response should be classified as "not evaluable", only when it is not possible to classify it under another response category, for example, when baseline and/or follow-up assessment is not performed or not performed appropriately.

Expert reviewers appointed by the Sponsor may undertake an independent review of the Investigator's assessed objective responses (CR and PR). The expert reviewers will include at least one specialist who is not an Investigator in the study. Any independent reviewer's assessment will also be documented in the final CSR along with the assessment made by the Investigator. The eCRF will reflect the Investigator's opinion.

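### Sections 3.5.1 and 13.6 leave early progressors without a repeat assessment out of the response-rate denominator, Section 10.3 counts them as non-responders, and the narrower set biases the rate upward

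*Protocol*

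**What the plan says.** Section 13.6 of the protocol defines the measure: "The response rate (proportion of evaluable patients with objective response) will be reported by cohort". The same section requires at least 66% of planned Cycle 1 and 2 exposure, or one full cycle, and says patients must "have a baseline assessment of disease and at least one repeat assessment to be evaluable for response". Section 3.5.1 sets the same condition: patients who meet the exposure rule and "have a baseline assessment of disease and at least one repeat disease assessment will be evaluable for response". In the expansion cohorts the baseline MT1-MMP H-score must also be positive.

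Section 10.3 opens with the same condition and then adds: "Patients who develop clear evidence of PD without a formal disease assessment will be considered non-responders". It also says: "Should rapid tumour progression occur before the completion of four weeks the patient will be classified as having early progression". Its not-evaluable category is a last resort, to be used "only when it is not possible to classify it under another response category", and one of its examples is a follow-up assessment that was not done.

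On replacement, Section 5.6.1.2 says: "Patients will be replaced in the expansion cohorts if they receive less than one full cycle and less than 66% of the planned dose exposure" in Cycles 1 and 2, unless the cause is drug-related toxicity.

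Section 13.1 sets the target at approximately 16 evaluable patients per cohort. It gives two benchmarks: 3 or more responses of 16 (10% versus 30%) and 5 or more of 16 (20% versus 40%), each at a significance level of 0.2 with 80% power. Activity in the first two cohorts is to be considered when deciding whether to open the oesophageal cohort.

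**The concern.** A patient with obvious clinical progression and no scan is outside the denominator under 3.5.1, 13.6 and the opening sentence of 10.3, and inside it as a failure under the later sentence of 10.3. An analyst cannot follow all of these, and the choice changes the reported rate.

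The exclusion also depends on outcome. A patient with no repeat assessment cannot be a confirmed responder, because complete and partial responses need confirmation at least four weeks later. A patient who stops after one or two doses is unlikely to be one. The patients removed are therefore almost entirely failures, and many of them are replaced by patients who last longer. At stake are the response rate compared with the benchmarks in 13.1 and one of the inputs to the decision on the oesophageal cohort.

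**Working it through.** **Passages side by side**

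| Patient | 3.5.1, 13.6, first sentence of 10.3 | Rest of 10.3 |
|---|---|---|
| Clear progression, no formal assessment | Not in denominator | Non-responder |
| Death without documented progression, no repeat scan | Not in denominator | No non-responder rule; not evaluable is allowed |
| Toxicity stop, no repeat scan | Not in denominator | No non-responder rule; not evaluable is allowed |
| Below the exposure threshold, scanned | Not in denominator | No rule unless progression falls before four weeks (early progression) |

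Only the first row is a direct contradiction.

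**Who falls below the threshold.** The once-weekly schedule gives 3 doses per cycle, so 6 in Cycles 1 and 2. 66% of 6 is 3.96 doses, and a full cycle is 3 doses. A patient who stops after one or two doses meets neither condition.

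**When the first scan is due.** It falls on Day 15 to 28 of the second 28-day cycle: 28 + 15 = study Day 43 to 28 + 28 = study Day 56.

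**The plan's own figures.** Exact binomial tails at n = 16:

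- P(X ≥ 3 | 0.10) = 0.211 and P(X ≥ 3 | 0.30) = 0.901
- P(X ≥ 5 | 0.20) = 0.202 and P(X ≥ 5 | 0.40) = 0.833

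The stated 0.2 and 80% are therefore nominal: both error rates are slightly above 0.2, and power is at least 80%. These exact values are the reference below.

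**Effect of dropping early failures.** Let p be the response rate in all dosed, marker-positive patients and d the share dropped, all assumed non-responders. The rate in the evaluable set is p / (1 − d). With recruitment continuing to 16 evaluable patients, the chance of passing is the binomial tail at that rate. The document gives no value for d, so 10% to 30% is an assumption.

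| d | 0.10 / (1 − d) | P(≥ 3 of 16) | 0.20 / (1 − d) | P(≥ 5 of 16) |
|---|---|---|---|---|
| 0 | 0.100 | 0.21 | 0.200 | 0.20 |
| 10% | 0.111 | 0.26 | 0.222 | 0.27 |
| 20% | 0.125 | 0.32 | 0.250 | 0.37 |
| 30% | 0.143 | 0.41 | 0.286 | 0.50 |

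The reported rate is multiplied by 1 / (1 − d), which is 1.11 at 10% and 1.43 at 30%. For example, with 4 dropped patients restored, 3/16 = 18.8% becomes 3/20 = 15.0%, and 5/16 = 31.3% becomes 5/20 = 25.0%.

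**Changing the denominator alone is not enough.** With 20 dosed patients and the same response counts, P(X ≥ 3 | 20, 0.10) = 0.323 and P(X ≥ 5 | 20, 0.20) = 0.370, as large as in the 20% row. The cut-off has to follow the denominator. At n = 20:

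- 4 or more: error rate 0.13 at 10%, power 0.89 at 30%
- 6 or more: error rate 0.20 at 20%, power 0.87 at 40%

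**The case against.** The progression sentence in 10.3 directly follows the evaluability sentence and can be read as a specific exception to it. That is a fair reading of 10.3 alone, but 3.5.1 and 13.6 do not carry the exception, and 13.6 is where the response rate is defined.

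Many early stoppers will be scanned. Section 7.2.2 allows earlier assessment on suspicion of progression, 7.3 asks for an off-study scan wherever possible (with exceptions), and 10.2.2 requires re-evaluation of patients removed for reasons other than progression. One full cycle meets the exposure rule. This stands, and it limits the share lost. It helps progressors least, because the 10.2.2 requirement does not cover them, and it does not rescue patients below the exposure threshold.

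Response is a secondary objective, data are presented descriptively, the benchmark rates in 13.1 are given as examples, and the oesophageal decision is a committee review, not a mechanical trigger. This also stands and lowers the severity.

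A reader might infer three stronger points that the protocol does not support:

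- **That 10.3 is contradicted for deaths and toxicity stops too.** Section 10.3 has no non-responder rule for them, and its not-evaluable example fits their exclusion.
- **That toxicity stops are neither replaced nor evaluable, so cohorts fall short of 16.** This can hold only for some of them; a patient who stops after a full cycle and is scanned is evaluable. The target is about 16 evaluable patients, and up to 70 are expected in Phase IIa against 3 × 16 = 48 for three cohorts.
- **That PFS and OS carry guaranteed event-free time.** Section 13.6 attaches the exposure and repeat-assessment conditions to evaluability for response. It measures PFS and OS from trial entry and does not restrict them to this set.

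**Conclusion.** The concern holds in a limited form. For patients with clear progression and no formal assessment, 3.5.1 and 13.6 conflict with 10.3, and 10.3 is at odds with its own opening sentence. For deaths and toxicity stops without a repeat scan, or before the exposure threshold, there is no contradiction, but their exclusion biases the response rate in the same direction.

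The direction is clear; the size cannot be derived from the document. The figures rest on three assumptions: 10% to 30% of dosed patients are lost, all of them are non-responders, and 16 evaluable patients are reached. On those terms the chance of passing at the undesirable rate is 0.26 to 0.41 for 3/16 and 0.27 to 0.50 for 5/16, against about 0.2 intended. If scans are obtained for most early stoppers and few fall below the exposure threshold, the effect will be nearer the low end or smaller. Severity: should be fixed.

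**What to change.** 1. Reconcile 3.5.1, 10.3 and 13.6. Define the main response set as expansion patients who received at least one dose and have a positive baseline MT1-MMP H-score. Count those who progress, die or stop for toxicity before a repeat assessment or before the exposure threshold as non-responders. A documented confirmed response after such short exposure would still count as a response.
2. Keep the current evaluable set as a supportive analysis.
3. State in 5.6.1.2 that replacing a patient for under-exposure adds a patient and does not remove the replaced one from this denominator. Patients with a low H-score stay outside it, as now.
4. In 13.1, restate the response cut-off for the actual denominator when it exceeds 16; the n = 20 values in the working are an example.

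The cost is wording only, with no change to treatment or data collection. The reported response rate will be somewhat less favourable and denominators may exceed 16.

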7.4.2 Efficacy and survival follow-up

Following pre screening informed consent, all patients should be followed up for survival until the end of the trial, where feasible, whether they subsequently start on trial treatment or not (Section 12). For those no longer on treatment, no further trial visits are required but the site trial team should check the status of the patient at least three monthly (through NHS/HSC electronic data records or by phone calls only if appropriate) until the patient starts another systemic anti-cancer therapy or when PD occurs (if not already occurred) and if the patient remains alive. End of trial may only be declared when all patients have either withdrawn from the trial, died, or completed a minimum of 12 months survival follow-up since their first administration of BT1718.

If the patient is lost to follow-up or has not progressed or died at the time of the final database lock for the Clinical Study Report (CSR), then the information will be censored as not known to have progressed/died at that time.

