10.2.2 Evaluations during and at 'off-study'

Tumour assessments must be repeated Day 15 – Day 28 of every two cycles or more frequently, when clinically indicated. All lesions measured at baseline must be measured at every subsequent disease assessment, and recorded clearly on the scan reports. All non-measurable lesions noted at baseline must be noted on the scan report as present or absent.

All patients who are removed from the trial for reasons other than PD must be re-evaluated at the time of treatment discontinuation, unless a tumour assessment was performed within the previous four weeks.

It is the responsibility of the Principal Investigator to ensure that the radiologists are aware of the requirement to follow-up and measure every target lesion mentioned at baseline and comment on the non-target lesions in accordance with RECIST 1.1 criteria.

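### PFS censoring is not tied to a tumour assessment while off-drug follow-up is remote, so the six-month PFS rate may be biased upward

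*Protocol*

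**What the plan says.** Section 13.6 counts PFS from trial entry to documented progression or death. Patients who are progression free or lost to follow-up at the analysis are "censored at the time the patient was last known to be alive and progression free". It promises median PFS and the six-month rate with 95% confidence intervals. Section 3.1.2 lists PFS and the six-month rate among the secondary endpoints.

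On drug, tumours are assessed every two 28-day cycles (7.2.2, 10.2.2). A patient who leaves for a reason other than progression "must be re-evaluated at the time of treatment discontinuation", with an exemption for a recent scan, and 7.3 likewise lists a scan at the off-study visit. Section 7.2.2 allows assessments to go on to progression or two years but does not require them once treatment has ended.

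For patients off treatment, 7.4.2 says "no further trial visits are required but the site trial team should check the status of the patient at least three monthly". The check is made from health-service electronic records, or by telephone where that is suitable. Footnote (n) of the schedule in 7.5.2 makes these checks the means of finding out when progression occurs.

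Section 7.4.2 also has its own sentence for patients lost to follow-up, or without an event at final database lock: "then the information will be censored as not known to have progressed/died at that time".

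**The concern.** The rule in 13.6 depends on what is known, and after the off-study scan the required source of knowledge is a record check or a phone call. If a call finds nothing recorded and that date becomes the censoring date, the months since the last scan count as progression free although nobody looked at the tumour. Progression found at a three-monthly check is also dated later than one found by an eight-weekly scan. Both effects push the six-month rate upward. The trial has no control arm to share the bias, and the confidence interval does not show it.

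The lock sentence in 7.4.2 adds a second description of censoring. It can be read as setting the lock date, or merely as describing the patient's status at that time.

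**Working it through.** The protocol states no PFS median, six-month target or PFS power, so there is no figure of its own to reproduce. The check sizes the bias under stated assumptions.

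**Inputs from the protocol**
- Scan interval on drug: 2 × 28 = 56 days = 1.84 months (7.2.2, 10.2.2).
- Last required scan: about 28 days = 0.92 months after stopping (7.3).
- Remote checks every 3 months (7.4.2).
- Follow-up of 12 months (12).
- Cohort of about 16 (13.1).

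**Assumptions not in the protocol**
- True PFS is exponential with median 2, 3, 4 or 6 months.
- Survival after progression has a median of 4 months.
- The nominal share s stopping without progression is 10%, 20% or 40%, with stopping hazard λs/(1−s), where λ = ln 2/median. The realised shares are 11–14%, 22–27% and 44–53%.
- Either none, half or all of the off-drug progressions are picked up at the next remote check. If missed, progression-free time runs to death or month 12.

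**Simulation** (200,000 patients per scenario, Kaplan-Meier). The entries are the six-month rate under remote-contact follow-up minus the rate had eight-weekly scans continued, in percentage points. The low end is all progressions picked up, the high end none.

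| Nominal share stopping without PD | Median 2 mo | 3 mo | 4 mo | 6 mo |
|---|---|---|---|---|
| 10% | +1.0 to +2.6 | +0.7 to +1.8 | +0.6 to +1.3 | +0.3 to +0.7 |
| 20% | +1.9 to +5.4 | +1.5 to +3.9 | +1.2 to +2.8 | +0.7 to +1.6 |
| 40% | +3.6 to +11.7 | +3.3 to +8.9 | +2.7 to +6.5 | +1.7 to +3.9 |

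Median PFS under the contact reading was equal to the continued-scan median or up to about 0.2 months lower. It was never higher.

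**Effect of scan-based censoring.** With true median 3 months, 20% stopping and half of progressions picked up, the six-month rate is 30.5% under the contact reading, 26.8% with censoring at the off-study scan and 27.9% with continued scans. Across scenarios, scan-based censoring lowers the contact figure by about 0.5 to 15 points. At 40% stopping it falls up to about 3 points below continued scanning. The median can also fall below the continued-scan median (4.34 against 5.52 months at true median 4, 40% stopping, none picked up). This simulated rule ignores deaths and progressions after the off-study scan.

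**Hand check at the unfavourable end.** Let k of 16 patients stop with a clear last scan at 1.84 months and no later progression be picked up. The time to month 6 is 6 − 1.84 = 4.16 months. The overstatement is (k/16)(a − q), where q is the probability of being truly progression free at six months and a that of being alive.
- Remaining median 2: q = 0.5^(4.16/2) = 0.2365; a = 2 × 0.5^(4.16/4) − q = 0.9726 − 0.2365 = 0.7361. The overstatement is 3.1 points for k = 1 and 9.4 for k = 3.
- Remaining median 4: q = 0.5^(4.16/4) = 0.4863; a = (1 + 0.7209) × 0.4863 = 0.8369. The overstatement is 2.2 points for k = 1 and 6.6 for k = 3.

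**Scale.** The standard error of a 25% rate in 16 patients is √(0.25 × 0.75/16) = 0.108, about 11 points.

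**The case against.** The best defence is that 13.6 never mentions a last contact. The event must be documented progression, response is judged by RECIST 1.1, and a patient may be known to be progression free only at an assessment. The SAP may fix the date. That reading is possible, but the protocol does not choose it, and footnote (n) points the other way by making remote checks a source of progression status. Because the protocol states a rule, the SAP should not have to override it.

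Several limits stand. Only patients who stop without progression are affected, since progression is itself a reason to stop (5.6). A record check may turn up a scan report, so remote follow-up is not always without imaging. PFS has no threshold; the benchmarks in 13.1 concern response.

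A reader might infer more than the documents support:
- That patients off drug have no trial scans. Sections 7.3 and 10.2.2 call for one on leaving.
- That PFS as a whole is overstated. The simulated median was not raised.
- That the six-month rate could be about 14 points too high, from 3/16 × (1 − 0.2365) = 14.3. This assumes that no affected patient dies and no progression is found, yet death is a PFS event.
- That the bias sits mainly in patients who stopped for toxicity. The protocol gives neither the share nor the reasons for stopping without progression.

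**Conclusion.** The concern holds as an ambiguous censoring rule that can be applied in a way that favours the drug. The six-month PFS rate may be biased upward, by a fraction of a point to about 5 points if roughly one patient in ten to one in four stops without progression, and by up to about 12 points if about half do and their progressions are missed. These sizes rest on the assumed PFS, post-progression survival, stopping and detection rates. In most scenarios the bias is well below the sampling error of a 16-patient cohort. With PFS secondary and descriptive, this is a minor point, worth correcting because it costs little.

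**What to change.** In 13.6, censor PFS at the date of the last evaluable RECIST 1.1 assessment without progression. Use record checks and phone contacts for survival, and for progression only when a scan or clinical report dates it. Say how a death or dated progression after the last scan is counted, because the simulated rule left these out and the remaining bias with them included was not calculated. Reword the database-lock sentence in 7.4.2 so that it gives the same censoring date as 13.6.

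This changes wording only and needs no extra scans or visits. The price is earlier censoring, somewhat wider intervals, and a possible downward shift relative to continued scanning: up to about 3 points in the six-month rate at 40% stopping without progression, and in some scenarios a lower median. Scan-based censoring removes the upward bias but does not replace continued imaging.
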